a different population (paroxysmal AF), we have not seen any adverse events related to the device over 6 months. The same TENS protocol will be followed in sham LLTS arm, but the electrode will be placed on the ear lobe, which is devoid of vagal innervation²³. The TENS unit will be set at a pulse width of 200 µs and a pulse frequency of 20 Hz. Amplitude will be titrated to the level of discomfort threshold, and will be set at 1 mA below that threshold. TENS will be applied for 1 hour daily for 3 months. After individual training, participants will apply TENS by themselves as part of their daily routine. Participants will be given a TENS unit to use at home. They will be instructed to return the unit at the end of the study. Participants will be requested to keep a daily log with the time and duration of TENS application, amplitude settings and any comments related to each daily session to monitor adherence. To ensure rigor and reduce biased self-report and outcome measurement, patients and investigators collecting study measurements will be blinded to the treatment allocation. Blinding of the patients will be accomplished by having a sham control arm, in which stimulation will be delivered to a different site (the ear lobe), devoid of vagal innervation²³. Thus, all patients will be aware that they are receiving stimulation, but they will not be told which site achieves active stimulation. The clinical coordinator, who is not collecting study measurements, will be unblinded to treatment allocation and will instruct the patients on the proper use of the device. Based on our experience from our ongoing study using LLTS in patients with paroxysmal AF, adherence to the stimulation protocol is >90%.

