Blood samples (10cc) will be collected from patients at baseline and 3 months for inflammatory cytokine measurement. At the baseline and 3 months subjects will be asked to complete the Minnesota Living With Heart Failure Questionnaire. At the 1 month visit, the patients will be interviewed by the unblinded physician or clinical coordinator to address any issues with TENS administration at home, and to assess their adherence to the stimulation protocol. A schematic representation of the study design is shown in Figure 5.

Data collection and analysis

Data will be collected by study personnel. Patients will be blinded to the treatment allocation, and every effort will be made to conceal from the study personnel the nature of the intervention in each study arm. The patients will be requested to refrain from discussing the details of their treatment with other patients in the clinic and with the physicians, nurses and the rest of clinic staff. The clinical coordinator and a clinic physician who will not participate in any of the other study related assessments will be unblinded to the treatment allocation and will instruct the patients

on the proper use of the device. These study personnel will be designated to address the patients' questions and concerns as well as to record any side effects related to the use of the device. The final data will be pooled and analyzed by the investigators.

Definition of outcomes

The coprimary outcomes at 3 months are 1) the ratio of the early mitral inflow Doppler velocity to the early diastolic mitral annulus velocity (E/e') and 2) global longitudinal strain (GLS). Secondary outcomes include other echocardiographic parameters [early diastolic mitral annulus velocity (e'), left atrial volume index, tricuspid regurgitation Doppler velocity, ratio of early to late mitral inflow Doppler velocity (E/A), global circumferential strain], 6-minute walk distance, quality of life (assessed by the Minnesota Living with Heart Failure Questionnaire). To ensure rigor, analysis and interpretation of the echocardiographic data, the 6-minute walk test data and inflammatory cytokine data will be performed in a blinded fashion.

Duration of participation:

Enrolled patients will participate in the study for 3 months.

Patient enrollment:

A maximum of 72 patients meeting the inclusion criteria and not meeting the exclusion criteria will be enrolled in the study. The enrollment period is expected to last for at least 18 months.

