Heart failure with preserved ejection fraction (HFpEF) has become a major public health concern. Epidemiological studies have shown that the prevalence and hospitalizations related to HFpEF are increasing, and the growing elderly population is expected to further worsen these trends. Outcomes of patients with HFpEF are poor, and so far, no treatment has been shown to decrease morbidity or mortality. If this therapy proves to be effective in reversing HFpEF, both study participants and others may benefit from this non-invasive treatment option with less risk involved. The results of this study may provide the basis for the design of human studies using this modality to target selected populations with HFpEF.

7. *Why risks are reasonable in relation to benefits:*

Heart failure with preserved ejection fraction (HFpEF) has become a major public health concern. Epidemiological studies have shown that the prevalence and hospitalizations related to HFpEF are increasing, and the growing elderly population is expected to further worsen these trends. Outcomes of patients with HFpEF are poor, and so far, no treatment has been shown to decrease morbidity or mortality. These proof-of-concept investigations will establish the first evidence of the effects of LLTS on HFpEF and may provide the basis for the design of further human studies using this modality to target selected populations with HFpEF. In light of the increasing number of patients with HFpEF and the poor success of the currently available treatment options, an alternative approach such as the one tested in this study, may benefit a large number of patients in Oklahoma.

H. Data and Safety Monitoring Plan

1. *Data and Safety Monitoring Plan (DSMP):*

An independent Data Safety Monitoring Board (DSMB) committee consisting of one cardiologist and one statistician will monitor the study. All adverse events will be reported to the DSMB committee. The committee will review recruitment and retention data, protocol adherence data, data quality, and safety data every 3-6 months.

a. *Reporting mechanisms for adverse events to the IRB, FDA, and NIH:*

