Clinical staff will track the following from patient report, physical assessments and documentation of clinical emergencies, adverse events according to federally published grading (0=no adverse event; 1=mild; 2=moderate; 3=severe and undesirable adverse events; 4=life threatening/disabling; or 5=death) and attribution (1=unrelated; 2=unlikely; 3=possible; 4=probable; 5=definite) scales. Clinical staff will report findings to the Investigator, who will then advise the IRB, NIH and FDA as indicated. Given the mild risk nature of the study, composite reports will be reviewed every ten patients to assure that untoward events do not occur systematically, and dropout cases will be reviewed singly to learn whether further inquiry or modifications should be made to improve study implementation.

b. Adverse event (AE) grading

0=no AE; 1=mild; 2=moderate; 3=severe and undesirable AE; 4=life threatening/disabling; or 5=death

c. Plan for unanticipated AE reporting:

Unanticipated AE will be reported to the IRB.

d. Plan for annual reporting of AEs:

Use of IRB forms for reporting. Our data sheet will have a column detailing any AEs that might occur.

e. *Interim efficacy analysis is not applicable to this study.*

2. *Data and Safety Monitoring Board (DSMB) that will be responsible for monitoring the study:*

- Institutional studies provide:
a. Chair, members

[name]

[name]

b. Frequency of safety reviews:

After each study

I. Literature sited

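### Unblinded staff record device side effects, the two adverse-event rules are not reconciled, and nothing makes attribution blind to allocation

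*Combined protocol and SAP*

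**What the plan says.** Blinding of outcomes is addressed directly. Section D, Aim 1, states that "patients and investigators collecting study measurements will be blinded to the treatment allocation". Elsewhere, section D has the echocardiographic, walk-test and cytokine data analysed blind.

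Device matters follow a separate route. Under Data collection and analysis in section D, "The clinical coordinator and a clinic physician who will not participate in any of the other study related assessments will be unblinded". This pair trains patients on the device and is designated to handle their questions and concerns "as well as to record any side effects related to the use of the device". The same paragraph asks patients not to talk about the details of their treatment with other clinic staff. At the 1-month visit "the patients will be interviewed by the unblinded physician or clinical coordinator to address any issues with TENS administration at home", and to assess adherence.

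Section H describes adverse events more broadly:

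- Item 1: "All adverse events will be reported to the DSMB committee".
- Item 1a: "Clinical staff will track the following from patient report, physical assessments and documentation of clinical emergencies, adverse events according to federally published grading", with "attribution (1=unrelated; 2=unlikely; 3=possible; 4=probable; 5=definite) scales". Findings then go to the Investigator.
- Item 1d: "Our data sheet will have a column detailing any AEs that might occur".

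Section D also has any cardiovascular event recorded at each follow-up visit, without naming the recorder. Section E plans a six-monthly summary of adverse events for the monitoring board and does not list them among the between-group comparisons.

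**The concern.** The section D rule makes relatedness a condition of the entry, and the person making the entry knows whether the clip is on the tragus or on the ear lobe, which the protocol regards as lacking vagal supply. Someone who believes that only the tragus site is active may probe harder for vagal-type symptoms in that arm, or attribute them more readily. The bias could also run the other way, if a recorder is slow to blame the device in the active arm.

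Attribution carries weight here. The effects listed under Risks in section G include dizziness, mild dyspnea and headaches. As a matter of clinical plausibility, HFpEF patients could report these without any stimulation, so calling one a device effect is a judgement. The protocol also relies on this kind of evidence itself: section D supports the device's safety by noting that no device-related adverse events had been seen in the ongoing atrial fibrillation study. If this trial's safety record is later used in the same way, device-attributed events are the quantity that knowledge of the arm can distort.

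**Working it through.** No figure in the plan bears on this point, so there is nothing to reproduce or recompute. The check sets the provisions side by side.

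| Provision | Who acts | Blinded? | Which events |
|---|---|---|---|
| Section D, Data collection and analysis | Coordinator and one clinic physician | No | Side effects related to the device |
| Section D, 1-month interview | The unblinded physician or the coordinator | No | Device problems and adherence |
| Section D, follow-up visits | Not named | Not stated | Any cardiovascular event |
| Section H, item 1 | Not named | Not stated | All adverse events, to the monitoring board |
| Section H, item 1a | Clinical staff, reporting to the Investigator | Not stated | Adverse events, graded 0-5 and attributed 1-5 |
| Section H, item 1d | Not named | Not stated | Any adverse event, on the data sheet |

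Step 1: is recording limited to related events? Not across the plan. The attribution scale starts at unrelated and unlikely, which makes sense only if such events are recorded. The data-sheet column, the reporting rule in item 1 and the cardiovascular-event rule carry no relatedness condition.

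Step 2: are the two routes consistent? They differ in order. Section D judges relatedness and then records. Section H records and then attributes. Nothing says which governs, or whether a side effect noted by the unblinded pair enters the section H process with its attribution already made.

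Step 3: is attribution blind anywhere? The blinding statements cover patients, those collecting study measurements, and the analysis of echocardiographic, walk-test and cytokine data. None covers grading or attribution of adverse events. The clinical staff in item 1a could include the unblinded pair, and the Investigator is not said to make or repeat the attribution blind.

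Step 4: does section H cure the section D route? Only in part. Patients' device concerns are directed to the unblinded pair, and patients are asked not to discuss treatment details with others. At month 1 the only named interviewer is unblinded. A non-cardiovascular symptom such as headache is therefore likely to reach someone who knows the arm first, and the board can be sent only what has been recorded.

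Step 5: what would be affected? Section D defines no safety outcome and section E no safety test. Section E does not say whether the adverse-event summaries are by arm. Any distortion would fall on descriptive counts of device-attributed events.

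**The case against.** The strongest reply is that section H already asks for all adverse events on a scale that includes unrelated ones, and that the section D routing is protective. Ear-site complaints reveal electrode placement, so sending them to staff who make no other assessments keeps outcome assessors blind. Both parts are correct. The second limits the remedy: routing device complaints to blinded outcome staff would put the efficacy blinding at risk. Neither part settles who attributes events, or whether that person knows the arm.

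A reader might infer three stronger things that the documents do not support:

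- That side effects are recorded only if judged related. This describes the section D sentence, not the plan; section H and the cardiovascular-event rule are broader.
- That the two unblinded people are the sole source of safety data. Item 1a names clinical staff generally, and the follow-up visits include a history and examination with no named recorder.
- That a planned active-versus-sham safety comparison is biased. No such comparison is specified.

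It is also tempting to put a number on a spurious gap between arms. That would need symptom rates and attribution probabilities that the documents do not give, and it would assume that unattributed events disappear from the record, whereas section H would log them as unrelated or unlikely.

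**Conclusion.** The point holds in a limited form. Section D gives the recording of device side effects to unblinded staff, with relatedness built into the instruction. Section H gives tracking and attribution to staff of unstated blinding. The two are not reconciled, and no section makes attribution blind.

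The consequence is a risk of biased elicitation and attribution of device-related events in the descriptive safety data. It is not a loss of all unrelated events, and it does not touch the coprimary outcomes, E/e' and global longitudinal strain, which are read blind. Neither the size nor the direction of the bias can be estimated from the documents.

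The conclusion assumes that safety will be described by arm at some stage, which the plan does not state but which would be usual for a sham-controlled trial. On that footing this is a worthwhile and inexpensive clarification, not a threat to the trial's main result.

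**What to change.** Amend Data collection and analysis in section D to agree with section H, items 1 to 1d:

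1. Record every adverse event before relatedness is judged, using one identical symptom checklist in both arms at months 1 and 3.
2. Let the unblinded coordinator and physician go on handling device problems, but have them pass events on in wording that masks the electrode site, for example a skin reaction under the electrode.
3. State in item 1a that grading and the 1-5 attribution are done by an investigator who is blinded to allocation and neither collects nor reads outcome measurements. The plan does not name such a person, so one of the existing investigators should be designated.

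The cost is protocol wording and one extra form. No visits are added, and the sample size and efficacy analyses do not change. A few more unrelated events will be logged. A small risk remains that local ear reactions unmask the attributing investigator, which is why that person should have no part in outcome measurement.

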Patients will be recruited from the outpatient clinics of the University of Oklahoma Health Sciences Center. Subjects will also be recruited through use of advertisement flyers distributed by campus email and posted in OUHSC clinics. Patients who view the study on ClinicalTrials.gov and have interest in study participation can approach us. They will contact the study coordinator using the telephone number that has been provided on the website. In addition, patients from the Oklahoma Heart Hospital, who meet all study inclusion criteria, will be referred to us by [name], Cardiologist. After informed consent, patients will be randomly assigned (1:1) to active or sham LLTS, stratified by gender. The randomization sequence will be created using randomly chosen block sizes of 4 or 6 and will be implemented through the online REDCap data system. The Parasym device (Parasym Inc) will be used for LLTS or sham stimulation. The device will be connected to a clip electrode that will be attached to the external ear. In the active group, the ear clip electrode will be attached to tragus in the active stimulation group (Figure 4). This device was deemed as non-significant risk by the FDA in our ongoing study (NCT02548274). Moreover, in our ongoing study using this device in

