Echocardiography will be performed at baseline and at 3 months to assess diastolic function (Acuson SC2000, Siemens). Two-dimensional long axis and short axis LV images will be obtained and Pulse-wave Doppler spectra of mitral inflow (E and A waves) and mitral annulus tissue Doppler spectra will be recorded. The early diastolic mitral annulus velocity (e') will be used to assess diastolic function as previously described^{24,25}. The ratio of early to late mitral inflow Doppler velocity (E/A ratio) is a marker of LV diastolic relaxation and stiffness, and the E/e' ratio correlates well with LV filling pressures^{24,25}. In addition, LV diastolic strain, a sensitive marker of diastolic LV function, which independently predicts outcomes in patients with HFpEF^{25,26}, will be obtained off-line using a speckle-tracking algorithm (Acuson SC2000 eSie VVI™). Analysis and interpretation of the echocardiographic data will be performed in a blinded fashion. A 6-minute walk test, a well validated measure of exercise capacity in heart failure²⁷, will be performed at baseline and 3 months. A 5-min ECG and a 10 second ECG will be performed at baseline and at 3 months to measure heart rate variability, a marker of vagosympathetic balance. To ensure rigor and avoid bias, participants will be encouraged to return for the 3-month post-treatment assessment regardless of their adherence status.

Aim 2. To examine the effect of intermittent (1 hour daily for 3 months) LLTS on inflammatory cytokines relative to sham stimulation, in patients with HFpEF.

[figure not shown]
The same group assignment described in Aim 1 will be used for Aim 2. Blood samples (10ml) will be collected at baseline and at 3 months for cytokine measurement. Samples will be centrifuged (4000g for 10 min), and serum will be stored in aliquots at -20°C until assayed. Patients' serum will be saved frozen and processed in batches of 10 to 12. Inflammatory cytokines, including TNF- α , IL-1 β , IL-6 and IL-18 will be measured using commercially available multiplex assays. In addition, RNA will be isolated from whole blood using the TempusTM RNA isolation tubes (ThermoFisher Scientific Inc., Waltham, MA), cDNA will be generated and gene expression of inflammatory cytokines and chemokines will be quantified using a Qiagen RT² Profiler PCR Array (PAHS-150Z), relative to the geometric mean of 5 stable reference genes. The investigators

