Data collection and analysis:

The final data will be pooled and analyzed by the investigators.

E. Statistical methods

Markers of inflammation, 6-minute walk distance and echocardiographic parameters will be compared between groups using repeated measures ANOVA, with 2 time points (baseline, 3 months) and 3 terms included in the model (group effect, time effect, group by time interaction). Significant interactions will be followed by time trend analyses stratified by intervention group. Transformations will be used as appropriate to satisfy modeling assumptions. Analyses will be based on the intention-to-treat principle. A separate per-protocol analysis, analyzing data from all patients who adhered to the TENS protocol at least 80% of the time, will also be performed. Sex will be investigated as a biologic variable by including sex, and interactions with sex, in the ANOVA model. Modification by sex will be explored and interpreted cautiously given that the pilot study is not powered to detect modification by sex. Gene expression array data will be analyzed using a Mann-Whitney U test, adjusting for multiple comparisons using the Benjamini-Hochberg method. Statistical significance will be set at $p<0.025$ for the 2 coprimary outcomes and at $p<0.05$ for all other data.

No formal interim efficacy analyses will be performed. Data quality and protocol implementation, as well as adverse events, will be summarized every six months for the DSMB.

Sample size and power calculations:

For purposes of sample size calculations we have simplified the analysis to focus on the difference in the E/e' ratio between the 2 intervention groups. Assuming a mean \pm standard deviation E/e'

ratio 11.1 ± 4.4 ²⁸ and 30% reduction in the LLTS group¹⁹, 72 patients would provide 80% power to detect the specified effect sizes at a two-sided α level of 0.025. The same sample size, under similar assumptions and a baseline GLS 16.1 ± 2.2 , would provide 90% power to detect an absolute 1.8% difference in GLS between the 2 groups.

F. Gender/Minority/Pediatric Inclusion for Research

Participants will be age 18 or older. Race, minority status and gender will not affect enrollment.

G. Human participants

72 participants of any gender/ethnic group, age 18 to 90 will be included.

Inclusion Criteria:

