1. Male and female patients older than 18 year old, diagnosed with HFrEF, defined according to the latest guidelines²² as signs and symptoms of heart failure, LV ejection fraction $\geq 50\%$, brain natriuretic peptide $\geq 35\text{pg/mL}$ and echocardiographic evidence of diastolic dysfunction (left atrial volume index $\geq 34\text{mL/m}^2$, mitral E-wave velocity/mitral annular velocity ratio $[\text{E}/\text{e}'] \geq 13$ and $\text{e}' < 9\text{cm/s}$)
2. Two of the following 4 comorbidities: 1. age ≥ 65 , 2. diabetes, 3. hypertension and 4. obesity, defined as body mass index $\geq 30\text{kg/m}^2$

Exclusion Criteria:

1. Left ventricular dysfunction (Left ventricular ejection fraction $< 40\%$)
2. Significant valvular disorder (i.e., prosthetic valve or hemodynamically significant valvular diseases)
3. Recent (< 30 days) stroke, myocardial infarction or hospitalization for heart failure
4. Severe heart failure (class IV)
5. End stage kidney disease
6. Recurrent vasovagal syncope
7. History of vagotomy
8. Pregnancy
9. Sick sinus syndrome and 2nd or 3rd degree AV block (without a pacemaker).

2. Sources of research material:

The research information will consist of echocardiographic parameters, ECG data, 6-minute walk distance, HRV parameters and inflammatory markers.

3. Plans for recruitment and consent procedures to be followed:

a. Location where consent is most likely to take place:

Patients will be recruited from the outpatient clinics of the University of Oklahoma Health Sciences Center. Patients who view the study on ClinicalTrials.gov and have interest in study participation will approach us. They will contact the study coordinator using the telephone number that has been provided on the website. In addition, patients from the Oklahoma Heart Hospital, who meet all study inclusion criteria, will be referred to us by [name], Cardiologist. The consent process will likely take place at the OU Physicians Cardiovascular Institute. All candidate subjects will have the purpose of the study explained to them, including the benefits and risks and options, prior to scheduled ablation procedure, will be asked to read the consent form, and after questions have been answered, will be asked to participate. Finally, they will be asked to sign the consent form.

b. Only English-speaking persons will be recruited. Non-English-speaking adults constitute less than 1% of the patients referred for ablation.

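### The planned two-visit repeated-measures ANOVA is a change-score test; adjusting for the baseline value already collected would be more precise for both coprimary outcomes, by an amount that depends on an unstated correlation

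*Combined protocol and SAP*

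**What the plan says.** Section E (Statistical methods) sets one model for the echo measurements, the walk test and the inflammatory markers, which are to be "compared between groups using repeated measures ANOVA, with 2 time points (baseline, 3 months) and 3 terms included in the model". The terms are group, time and group by time. Significant interactions lead to time-trend analyses within each arm, which implies that the interaction carries the treatment test, although the section does not say so. Sex and its interactions are to be added to the ANOVA in an exploratory look at effect modification. No section uses the baseline value of an outcome as a covariate.

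The baseline value will exist. Section D, Aim 1, says "Echocardiography will be performed at baseline and at 3 months to assess diastolic function". Under Definition of outcomes the targets are 3-month values: "The coprimary outcomes at 3 months are 1) the ratio of the early mitral inflow Doppler velocity" to the annular velocity (E/e'), and 2) global longitudinal strain (GLS). Section D also says "patients will be randomly assigned (1:1) to active or sham LLTS, stratified by gender".

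The power statement does not use the planned model: "For purposes of sample size calculations we have simplified the analysis to focus on the difference" in E/e' between the two arms. For GLS it says that the same sample size "would provide 90% power to detect an absolute 1.8% difference in GLS between the 2 groups". It uses single-visit SDs and gives neither a correlation between visits nor an SD of change.

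**The concern.** The planned model treats baseline as a second outcome rather than as a predictor. For two visits this amounts to analysing change, which subtracts the whole baseline value whatever the correlation. When the correlation is modest, that subtraction adds noise. ANCOVA estimates how much of the baseline to subtract.

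The plan's power figures come from a comparison of single-visit values. The planned test has the same power as that comparison only at rho 0.5 and falls below it at any lower rho. The enrolment limit ("A maximum of 72 patients meeting the inclusion criteria and not meeting the exclusion criteria will be enrolled in the study") means that lost precision cannot be recovered with more patients, and no allowance for dropout is stated.

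Leaving the test term unnamed adds a smaller risk. The group main effect in the same model averages in the baseline visit and halves the treatment effect. At rho 0.5 it would have only about 35% power for E/e' and 41% for GLS (normal approximation).

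**Working it through.** **Inputs from the protocol (section E unless noted).** Total 72, allocated 1:1 (section D), so 36 per arm. Two-sided alpha 0.025 for each coprimary outcome. E/e': SD 4.4, difference 30% of 11.1 = 3.33. GLS: SD 2.2, difference 1.8.

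**Assumptions.** Rho is not given; 0.3, 0.5, 0.7 and 0.8 are shown. SDs are equal at the two visits. All 72 complete, which is a best case.

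**1. The plan's own figures.** Two independent means, 36 per arm, single-visit SD:
- E/e': 81.9% by noncentral t, 83.4% by normal approximation (stated 80%).
- GLS: 87.8% by noncentral t, 89.1% by normal approximation (stated 90%).

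Each stated figure is reproduced to within 2 points by one of the two standard methods.

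**2. Equivalence.** On a generated data set with 36 per arm, the group-by-time F and the squared t on change scores were both 3.3148, on 70 df.

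**3. Variances per patient.**
- Change score: 2(1 - rho) x SD².
- ANCOVA: (1 - rho²) x SD².
- Ratio: (1 + rho)/2 = 0.65, 0.75, 0.85, 0.90 at rho 0.3, 0.5, 0.7, 0.8.

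If the SDs differ between visits, the change-score variance exceeds the ANCOVA variance by (SD at baseline - rho x SD at 3 months)², which cannot be negative.

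Example, GLS at rho 0.5: the change-score SD is 2.2 x sqrt(1.00) = 2.20 and the ANCOVA SD is 2.2 x sqrt(0.75) = 1.91.

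**4. Power and precision.** Noncentral t, with 70 df for change and 68 df for ANCOVA with baseline and sex. The half-width of the 97.5% CI is t x SD x sqrt(2/36). Each cell is change score vs ANCOVA.

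| rho | GLS power | GLS half-width | E/e' power | E/e' half-width |
|---|---|---|---|---|
| 0.3 | 74% vs 91% | 1.41 vs 1.13 | 66% vs 86% | 2.81 vs 2.27 |
| 0.5 | 88% vs 95% | 1.19 vs 1.03 | 82% vs 92% | 2.38 vs 2.06 |
| 0.7 | 98.5% vs 99.4% | 0.92 vs 0.85 | 96.6% vs 98.5% | 1.84 vs 1.70 |
| 0.8 | 99.9% vs 99.97% | 0.75 vs 0.71 | 99.7% vs 99.9% | 1.50 vs 1.43 |

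To match ANCOVA on 72 patients, the change-score test would need 72 x 2/(1 + rho) = 111, 96, 85 and 80 patients (ignoring degrees of freedom).

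**5. Simulation check.** 20,000 trials per setting, ANCOVA including sex, at rho 0.3, 0.5 and 0.7. GLS: 74.4 vs 90.6%, 87.9 vs 95.2%, 98.6 vs 99.4%. E/e': 66.9 vs 85.1%, 81.5 vs 91.1%, 96.8 vs 98.4%. Type I error was 2.3 to 2.7% for both methods. The formula makes ANCOVA look up to about 1 point better than the simulation because it ignores chance imbalance in the covariates.

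**6. Fewer completers.** With 32 per arm (assumed), at rho 0.3, 0.5 and 0.7:
- GLS: 68% vs 87%, 83% vs 93%, 97.1% vs 98.8%.
- E/e': 60% vs 81%, 77% vs 88%, 94.4% vs 97.2%.

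**7. The E/e' entry limit.** The inclusion criteria in section G require a "mitral E-wave velocity/mitral annular velocity ratio" of at least 13. Suppose this cuts the baseline echo itself and the uncut distribution is normal with mean 11.1 and SD 4.4. The enrolled baseline then has mean 15.9 and SD 2.33.
- Change variance: (1 - rho)² x 2.33² + (1 - rho²) x 4.4².
- ANCOVA variance: (1 - rho²) x 4.4².
- Ratio at uncut rho 0.3, 0.5, 0.7: 0.87, 0.91, 0.95. The correlation in the enrolled sample falls to 0.16, 0.29, 0.46.
- Power for a difference of 3.33: 80% vs 86%, 89% vs 92%, 98.1% vs 98.5%.
- If the 30% reduction is taken from the enrolled mean (0.30 x 15.9 = 4.77), both tests exceed 98%.

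**The case against.** The strongest reply is that nothing here is wrong. The trial is a pilot, the planned model is recognised and valid, and the case for change rests on a correlation that nobody has stated. At rho 0.7 both tests already have more than 96% power for both outcomes. The large contrasts need rho near 0.3, and nothing in the protocol supports that value. All of this stands: the direction of the gain is certain and its size is not, so the rho 0.3 figures should not be read as the expected loss.

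The protocol does contain paired strain data. The crossover pilot of 10 patients (sections B and C) reports a within-patient difference of 2.7 ± 1.4 with ± 2.4 in each condition. If all the ± values are of the same kind, rho = 1 - 1.4²/(2 x 2.4²) = 0.83, where the power gain is negligible. This does not settle the matter. The sessions could be one day apart, not 3 months. The ± values also fit the reported p = 0.05 poorly as SDs (paired p about 0.0002). Read as standard errors they fit better, but imply a single-session SD of 2.4 x sqrt(10) = 7.6, against 2.2 in the power statement.

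For E/e', section D lists three visits and no separate screening echo, so the limit of 13 may well apply to the baseline measurement. The smaller gain in step 7 would then be the relevant one. The protocol does not say, so both cases are shown.

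Finally, sex is already in the ANOVA plan. It is there to explore effect modification, not as the stratification factor in the primary test.

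**Conclusion.** The point holds. The planned test of the coprimary outcomes, read as the group-by-time interaction, is a change-score t-test, and it leaves precision unused. This is an inefficiency, not an error.

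Under equal SDs, ANCOVA variance is lower by 35%, 25%, 15% and 10% at rho 0.3, 0.5, 0.7 and 0.8. The power gain is substantial at or below rho 0.5, small at 0.7 and almost nil from 0.8, where only a confidence interval about 5% narrower remains. ANCOVA has more power than the plan's simplified comparison at every rho shown, whereas the planned test has less below 0.5. ANCOVA therefore protects the stated power against not knowing rho.

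The figures assume 72 completers, the plan's SDs and equal SDs at both visits. For E/e' the gain is smaller if the entry limit truncates the baseline echo. The change is worth making because it is almost free, even though its benefit cannot be fixed in advance.

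**What to change.** In section E, name one primary test for each coprimary outcome: ANCOVA of the 3-month value on treatment, baseline value and sex (the randomisation stratum), with the treatment coefficient tested at two-sided 0.025. Report the adjusted difference with its confidence interval. Use the same model for the continuous secondary outcomes and the cytokines, on the transformed scale where the planned transformations apply. Keep the sex-by-treatment interaction as a separate exploratory analysis.

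State the assumed correlation in the power section, or show power over a range of values, and say whether the E/e' entry limit is judged on the baseline echo.

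The cost is SAP wording and two degrees of freedom. No new data, visits or patients are needed.
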